Attachment 2: Toxicity Tables

Adapted from the FDA Guidance document “Toxicity Grading Scale for Healthy Adult and Adolescent Volunteers Enrolled in Preventive Vaccine Clinical Trials” (September 2007).

Local Reaction to Injectable Product	Mild (Grade 1)	Moderate (Grade 2)	Severe (Grade 3)	Potentially Life-threatening (Grade 4)
Pain/Tenderness	Aware of symptoms but easily tolerated; Does not interfere with activity; Discomfort only to touch	Notable symptoms; Requires modification in activity or use of medications; Discomfort with movement	Incapacitating symptoms; Inability to do work, school, or usual activities; Use of narcotic pain reliever	Hospitalization; Pain/tenderness causing inability to perform basic self-care function;
Erythema	25 – 50 mm	51 – 100 mm	> 100 mm	Hospitalization; Necrosis or exfoliative dermatitis
Swelling	25 – 50 mm	51 – 100 mm	> 100 mm	Hospitalization; Necrosis

Vital Signs *	Mild (Grade 1)	Moderate (Grade 2)	Severe (Grade 3)	Potentially Life-threatening (Grade 4)
Fever** (°C) Fever** (°F)	38.0 – 38.4 100.4 – 101.1	38.5 – 38.9 101.2 – 102.0	39.0 – 40 102.1 – 104	>40 >104
Tachycardia - beats per minute	101 – 115	116 – 130	>130	Hospitalization for arrhythmia
Bradycardia - beats per minute***	50 – 54	45 – 49	<45	Hospitalization for arrhythmia
Hypertension (systolic) - mm Hg	141 – 150	151 – 160	>160	Hospitalization for malignant hypertension
Hypertension (diastolic) - mm Hg	91 – 95	96 – 100	>100	Hospitalization for malignant hypertension
Hypotension (systolic) – mm Hg	85 – 89	80 – 84	<80	Hospitalization for hypotensive shock
Respiratory Rate – breaths per minute	17 – 20	21 – 25	>25	Intubation

* Participant should be at rest for all vital sign measurements.

** For oral temperature: no recent hot or cold beverages or smoking.

*** When resting heart rate is between 60 – 100 beats per minute. Use clinical judgement when characterizing bradycardia among some healthy participant populations, for example, conditioned athletes.

Systemic (General)	Mild (Grade 1)	Moderate (Grade 2)	Severe (Grade 3)	Potentially Life-threatening (Grade 4)
Vomiting	No interference with activity or 1-2 episodes/24 hours	Some interference with activity or >2 episodes/24 hours	Prevents daily activity, requires outpatient IV hydration	Hospitalization; Hypotensive shock
Nausea	Minimal symptoms; causes minimal or no interference with work, school, or self-care activities.	Notable symptoms; Requires modification in activity or use of medications; Does NOT result in loss of work, school, or cancellation of social activities.	Incapacitating symptoms; Requires bed rest and/or results in loss of work, school, or cancellation of social activities.	Hospitalization; Inability to perform basic self-care functions.
Diarrhea	2 – 3 loose stools or <400 gms/24 hours	4 – 5 stools or 400-800 gms/24 hours	6 or more watery stools or >800 gms/24 hours or oral rehydration necessary	Hospitalization; Hypotensive shock or IV fluid replacement indicated
Headache	Minimal symptoms; causes minimal or no interference with work, school, or self-care activities.	Notable symptoms; Requires modification in activity or use of medications; Does NOT result in loss of work, school, or cancellation of social activities.	Incapacitating symptoms; Requires bed rest and/or results in loss of work, school, or cancellation of social activities; Use of narcotic pain reliever.	Hospitalization; Inability to perform basic self-care functions.
Fatigue	Minimal symptoms; causes minimal or no interference with work, school, or self-care activities.	Notable symptoms; Requires modification in activity or use of medications; Does NOT result in loss of work, school, or cancellation of social activities.	Incapacitating symptoms; Requires bed rest and/or results in loss of work, school, or cancellation of social activities; Use of narcotic pain reliever.	Hospitalization; Inability to perform basic self-care functions.
Myalgia	Minimal symptoms; causes minimal or no interference with work, school, or self-care activities.	Notable symptoms; Requires modification in activity or use of medications; Does NOT result in loss of work, school, or cancellation of social activities.	Incapacitating symptoms; Requires bed rest and/or results in loss of work, school, or cancellation of social activities; Use of narcotic pain reliever.	Hospitalization; Inability to perform basic self-care functions.

Systemic Illness	Mild (Grade 1)	Moderate (Grade 2)	Severe (Grade 3)	Potentially Life-threatening (Grade 4)
Illness or clinical adverse event (as defined according to applicable regulations)	No interference with activity	Some interference with activity not requiring medical intervention	Prevents daily activity and requires medical intervention	Hospitalization

Attachment 3: Clinical Assessment

CLINICAL QUESTIONNAIRE	
Participant ID:	

VITAL SIGNS	
Temperature (°C/°F)	
Blood pressure (SBP/DBP)	
Heart rate (bpm)	
Respiratory rate (breaths per minute)	
Oxygen saturation (SpO ₂)	

PHYSICAL EXAMINATION SCORING				
Level	0	1	2	3
	No Symptoms	Just noticeable	Bothersome sometimes, not interfering with other activities	Bothersome most of the time, interfering with other activities
Cough				
Sputum production				
Shortness of breath				
Malaise (tiredness)				

UPPER RESPIRATORY				
Level	0	1	2	3
Nasal Discharge	None	Clear, serous: scant but slightly increased	Clear to white, obvious increased volume, + minor blood streaks on tissue	Frankly purulent (yellow or green), or gross blood
Pharyngitis	None	Mild and/or patchy erythema	Marked and/or confluent erythema	Erythema and purulent exudate
Sinus Tenderness	None		Mild tenderness	Severe tenderness or overlying erythema

LOWER RESPIRATORY				
Level	0	1	2	3
Dyspnea	None	May have brief episodes	May have increased episodes	May have severe episodes
Rales, rhonchi or other	None		Scattered wheezes or rhonchi	Widespread wheezes or rhonchi, rales, dyspnea, or signs of consolidation
Wheezing	None	Terminal expiration or only with stethoscope	Entire expiration or audible on expiration without stethoscope	Inspiration and expiration without stethoscope
Respiratory Effort	None	Mild chest wall retraction	Trachea tug with moderate chest wall retraction and nasal flare	Marked chest wall retraction with nasal flare

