9.2.1.4. Clinical Assessment

At baseline, and between 2 and 4 days after symptom onset (ARI Days 3-5) and at ARI Day 29, a study staff member will perform a clinical assessment ([Attachment 3](#)):

- Vital signs: body temperature, systolic and diastolic blood pressure, heart rate, respiratory rate, and oxygen saturation measurement.
- Symptom collection and targeted physical examination: cough, sputum production, shortness of breath, and malaise (tiredness)
- Upper respiratory: nasal discharge, pharyngitis, and sinus tenderness
- Lower respiratory: dyspnea, rales, rhonchi or other, wheezing, and respiratory effort

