11.4. Efficacy Analyses

11.4.1. Primary Efficacy Endpoints

Three primary efficacy endpoints are defined as follows:

- First occurrence of RT-PCR-confirmed RSV-mediated LRTD according to Case Definition #1
- First occurrence of RT-PCR-confirmed RSV-mediated LRTD according to Case Definition #2
- First occurrence of RT-PCR-confirmed RSV-mediated LRTD according to Case Definition #3

The case definitions are defined as follows:

Case Definition #1	Case Definition #2	Case Definition #3
≥3 symptoms of LRTI (new onset or worsening)	≥2 symptoms of LRTI (new onset or worsening)	≥2 symptoms of LRTI, OR ≥1 symptom of LRTI combined with ≥1 systemic symptom
		(new onset or worsening)

LRTI = lower respiratory tract infection

To meet the primary endpoint according to the respective case definitions the following criteria will be taken into account:

- symptoms reported by participants on the RiiQ Symptom Scale and body temperature during the full ARI episode OR
- clinical assessment terms reported by a qualified study staff member during the ARI Days 3-5 clinical visit

in combination with

- confirmation of RSV by RT-PCR in one or more of the midturbinate nasal swabs, or in the sputum sample (when available)

Of note, on the day of the ARI Days 3-5 clinical visit, the case definitions can be met by symptoms reported by participants on the RiiQ or by signs and symptoms reported by the qualified study staff member. Case definitions cannot be met by a combination of symptoms reported by the participant with signs and symptoms reported by the qualified study staff member.

Confirmation of RSV infection by RT-PCR (midturbinate swabs and sputum sample, when available) will be performed at the central laboratory. For participants hospitalized with symptoms of an ARI, confirmation of RSV infection using an FDA-approved RT-PCR test at the local (hospital) laboratory will also be used for the analysis of case definitions if results from the central laboratory are not available. One positive sample (defined as any sample with a value above the limit of detection) is sufficient.

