As a sensitivity analysis, the analysis of the primary endpoint will be repeated, but participants with RSV infection and a co-infection with at least one other respiratory virus (ie, confirmed using an FDA approved RT-PCR test in one or more of the midturbinate nasal swabs, or in the sputum sample, when available) will not be considered as a case for that episode, as the etiology of the symptoms will be indeterminate.

As an additional sensitivity analysis, the analysis of the primary endpoint will be repeated, taking into account only the RT-PCR test results from the central laboratory (ie, excluding the local test results for hospitalized participants).

Presence and severity of symptoms will be collected using participant responses to the RiiQ Symptom Scale and temperature readings participants report in the eDiary each day throughout each ARI episode. On the day of the ARI Days 3-5 clinical visit, signs and symptoms will also be collected by qualified study staff in a clinical assessment.

Table 11: Symptoms of Lower Respiratory Tract Infection and Systemic Symptoms as per RiiQ or Clinical Assessment

	Symptoms from Case Definition	RiiQ Term	Clinical Assessment Term (ARI Days 3-5 Clinical Visit)
Symptoms of LRTI	Cough	Cough	Cough
	Shortness of breath	Short of breath	Dyspnea or decreased oxygen saturation*
	Sputum production	Coughing up phlegm (sputum)	Sputum production
	Wheezing	Wheezing	Wheezing; rhonchi, rales or other sign of consolidation
Systemic Symptoms	Tachypnea**		Tachypnea
	Fatigue	Fatigue (tiredness)	Malaise (tiredness)
	Fever***,****		Fever
	Feverishness****	Feeling feverish	

* Decreased oxygen saturation is defined as oxygen saturation of <90% for participants with a baseline oxygen saturation of $\geq 90\%$ at randomization; for participants with baseline oxygen saturation <90%, decreased oxygen saturation is defined as a $\geq 3\%$ decrease in their oxygen saturation from baseline.

** Tachypnea is defined as respiratory rate >20 breaths per minute.

*** Fever (ie, temperature >37.8°C) will be reported via daily temperature measurement and during ARI Days 3-5 clinical visit.

**** Feeling feverish and fever are considered as 1 symptom.

LRTI =lower respiratory tract infection, RiiQ = Respiratory Infection Intensity and Impact Questionnaire

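### Attachment 3 and Table 11 treat dyspnea inconsistently, so one staff finding could be counted as two LRTI symptoms in the primary case definitions

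*Protocol*

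**What the plan says.** Section 9.2.1.4 lists the staff-assessed items: "Lower respiratory: dyspnea, rales, rhonchi or other, wheezing, and respiratory effort". In Attachment 3 each of these is a separate row scored 0 to 3.

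- The Dyspnea row has its own anchors, up to "May have severe episodes" at Level 3.
- The rales/rhonchi row has the Level 3 anchor "Widespread wheezes or rhonchi, rales, dyspnea, or signs of consolidation". The entries are alternatives, and the row yields one score.

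Table 11 in Section 11.4.1 translates staff findings into LRTI symptoms. Shortness of breath is met by "Dyspnea or decreased oxygen saturation". Wheezing is met by "Wheezing; rhonchi, rales or other sign of consolidation".

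Section 11.4.1 lets a case definition be met on "clinical assessment terms reported by a qualified study staff member during the ARI Days 3-5 clinical visit", without help from the participant's RiiQ entries, provided RSV is confirmed by RT-PCR. Symptoms must be new or worse than baseline, and those present on the same day are added up. Case Definition #1 needs at least three LRTI symptoms. #2 needs at least two. #3 needs two, or one with a systemic symptom. The only rule in Table 11 that merges two overlapping entries concerns fever and feverishness.

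**The concern.** The two places disagree about what a score in the rales/rhonchi row can mean. Table 11 reads it as a chest sign, while the form allows it to be dyspnea. Dyspnea is the one word in that anchor that belongs to a different counted symptom. Wheezes also appear in two rows, but both lead to Wheezing, so that overlap does no harm.

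The three definitions are separated mainly by the number of LRTI symptoms, and the ordinal endpoint in Table 12 (Section 11.4.3) uses the same count. One spurious symptom moves an episode up a step. Section 1.2 gives selection of a case definition for Phase 3 as a purpose of testing the three side by side, so a count that can be inflated by one duplicated finding weakens that comparison as well as the endpoint itself.

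**Working it through.** The protocol gives no figure for this point, so there is nothing to reproduce. The check applies Table 11 and the case definitions to the form.

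**Counting rule used.** Shortness of breath = Dyspnea row above 0, or decreased saturation. Wheezing = Wheezing row above 0, or rales/rhonchi row above 0. Crediting any score in the rales/rhonchi row to Wheezing is an assumption, because the protocol does not state which form row feeds which term. All findings are taken as new, with no other lower respiratory finding.

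| Staff findings | Rales/rhonchi row | LRTI symptoms | #1 | #2 | #3 |
|---|---|---|---|---|---|
| Dyspnea only | 0 | 1 | no | no | only with a systemic symptom |
| Dyspnea only | 3, because of dyspnea | 2 | no | yes | yes |
| Cough and dyspnea | 0 | 2 | no | yes | yes |
| Cough and dyspnea | 3, because of dyspnea | 3 | yes | yes | yes |

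On the ordinal scale of Table 12, dyspnea with a systemic symptom would move from 2 to 3, and cough plus dyspnea from 3 to 4.

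**Which episodes can change.** All of these must hold: RT-PCR positive; assessed by staff at ARI Days 3-5; findings new or worse than baseline; Level 3 ticked because of dyspnea, with no independent reason to credit Wheezing; and the definition not already met on RiiQ on any day of the episode.

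**Possible dilution of VE (assumed range).** Let *f* be the share of placebo #2 cases that arise only through the duplicate, and VE_x the efficacy against them. With the planning value of 70% (Section 11.2.1) against the rest:

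observed VE = 1 − [(1 − f) × 0.30 + f × (1 − VE_x)]

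- VE_x = 0: f = 5% gives 1 − (0.285 + 0.05) = 66.5%; f = 10% gives 1 − (0.27 + 0.10) = 63%; f = 20% gives 1 − (0.24 + 0.20) = 56%.
- VE_x = 35%: about 68%, 66.5% and 63%.
- VE_x = 70%: no dilution.

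The documents give neither *f* nor VE_x.

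**Sensitivity of the test to one case (illustration).** Section 11.2.1 expects 26 cases, and the worked interim example in Section 11.4.1.1 has 18 #2 events and a cut-off of 0.0175. An unstratified 1:1 exact binomial is used here as a stand-in for the planned exact Poisson model. A split of 4 v 14 gives one-sided p = 4,048/262,144 = 0.0154. Adding one vaccine-arm case, 5 v 14 gives 16,664/524,288 = 0.0318.

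**The case against.** The strongest reply is that Table 11 lists signs, not form rows. It places dyspnea under Shortness of breath and does not name it under Wheezing, so on its own wording dyspnea alone is one symptom. The double count needs two further steps: an assessor who hears a clear chest ticks the top score of a row about chest sounds, and the derivation credits that score to Wheezing. The first is a strained reading by staff who are preferably physicians, physician assistants or nurse practitioners (Section 9.1.1). The second is a derivation detail that may be settled in the SAP. This stands, and it is why the point is an inconsistency with a possible consequence and not a demonstrated double count. It does not remove the problem: a Level 3 score does not record which alternative produced it, so a derivation cannot recover Table 11's distinction from that score.

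The RiiQ route also limits the reach, because many episodes may already qualify through it. That stands too.

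The Clinical Evaluation Committee described in Section 11.4.3 assesses location and severity independently. That helps in interpreting the definitions, but the protocol uses it to explore their relation with severity and does not say that it alters primary case status.

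Finally, the last season's ARI onset cut-off was 15 April 2022 (Section 3.1), before Amendment 8 of 16 February 2023. A form change now cannot affect this trial's efficacy data. That is correct, and the fix is divided accordingly.

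**Conclusion.** The inconsistency is in the text. Its effect is conditional: one extra LRTI symptom per affected episode, enough to create a #2 or #3 case from dyspnea alone, or a #1 case from cough plus dyspnea. How many episodes are affected cannot be known from the protocol.

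Three stronger readings are not supported.

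- A reader might infer that the plan does double count dyspnea. It does so only if Level 3 is ticked for dyspnea and the row is credited to Wheezing.
- A reader might infer bias towards one arm. Site staff were blinded to the Day 1 allocation (Section 5), so the error should be non-differential. The expected costs are loss of specificity, possible dilution of VE and less distinct definitions.
- A reader might infer that the proof-of-concept result hangs on it. The 4 v 14 example shows only that, with few events, a single case can matter. The split is invented, and the 0.0175 cut-off belongs to the protocol's worked interim example, not to a fixed threshold.

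The point is worth acting on because it touches the primary endpoints and a single rerun can show how much depends on it.

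**What to change.** **Reconcile the form and the table.** Remove dyspnea from the Level 3 anchor of the rales/rhonchi row, so that the row records only what Table 11 credits to Wheezing. This is relevant to any further use of the form, such as in Phase 3. It costs one word on the form.

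**For data already collected, add one sensitivity analysis.** Apply it to the three primary endpoints and the ordinal endpoint. Where the Dyspnea row is scored, the Wheezing row is 0 and the rales/rhonchi row is 3, count one LRTI symptom instead of two. Rerun the full case algorithm, including the RiiQ route, and report by arm how many cases change under each definition. If none change, the matter is closed. The cost is one extra derivation and one rerun.

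**Downside to state with it.** Genuine rales or consolidation together with dyspnea can be recorded in the same way, so the rule also merges some true second signs. It is a conservative bound on the cases that depend on the ambiguity and should not replace the primary analysis. Participants whose wheeze was present at baseline and unchanged fall outside the rule and should be listed separately.

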Attachment 4: ARI Surveillance Assessment

Since the last time you completed your eDiary, have you had any symptoms of a cold or respiratory infection such as a stuffy or runny nose (nasal congestion), a sore throat, a cough, coughing up phlegm (sputum), trouble breathing, or whistling sounds when you breathe (wheezing)?

If you usually have some of these symptoms even when you do not have a cold, please only answer “yes” if you have more symptoms than usual or your symptoms are worse than usual.

Responses:

No cold symptoms *The participant will be referred to AE reminder screen (below)*

Yes, I had cold symptoms *The participant completes ARI assessment as follows:*

1. Date ARI symptoms started or became worse than usual
2. RiiQTMv2 Symptom Scale

The ePRO system will compare reported symptoms/severity to values reported during the vaccination visit.

If symptoms are the same or less severe than the participant reported during the vaccination visit, the symptoms indicate no ARI has occurred according to protocol definition. Therefore, the remainder of the ARI assessment is not collected. The participant will be referred to AE reminder screen (below).

If symptoms are worse than baseline, the remaining ARI assessments are presented in the following order^a:

3. RiiQTMv2 Impact on Daily Activities
4. PGI-H
5. PGI-S
6. PGI-C
(Note that the PGI C will not be completed on ARI Day 1)
7. Return to Usual Health
(Note that the Return to Usual Health question will not be completed on ARI Day 1)
8. Temperature Log

The participant will then be referred to AE reminder screen (below). A final screen reminds participants to collect a nasal swab and to contact site to schedule a site visit.

AE Reminder Screen:

Thank you for completing your eDiary.

If you are having any severe symptoms, health issues, or other concerns about your health, please contact your study doctor to discuss these.

^a The RiiQTMv2 Impact on Daily Activities, PGI-H, PGI-S, PGI-C, Return to Usual Health, and temperature log assessments are part of the Combined Impact Assessment.

Attachment 5: Respiratory Infection Intensity and Impact Questionnaire (RiiQ™v2) – Symptom Scale

Please read each of the following questions and select the answer thinking about when you felt the worst in the past 24 hours.

During the past 24 hours, have you had the following symptoms?

	None	Mild	Moderate	Severe
a. Cough				
b. Sore throat				
c. Headache				
d. Nasal congestion				
e. Feeling feverish				
f. Body aches and pains				
g. Fatigue (tiredness)				
h. Neck pain				
i. Interrupted sleep				
j. Wheezing				
k. Coughing up phlegm (sputum)				
l. Short of breath				
m. Loss of appetite				

Question 1 of the Respiratory Infection intensity and impact questionnaire (RiiQ™) ©RH Osborne (2006, 2018).
 No part of the RiiQ™ may be copied or reproduced in any form without written permission from
 RH Osborne PhD:[contact]
 (Variable recall Version. English. Administered under license by Janssen Pharmaceuticals).
 (English – administration once daily)

Attachment 6: Respiratory Infection Intensity and Impact Questionnaire (RiiQ™v2)

Please read each of the following questions and select the answer thinking about when you felt the worst in the past 24 hours.

Symptoms**1. During the past 24 hours, have you had the following symptoms?**

	None	Mild	Moderate	Severe
a. Cough				
b. Sore throat				
c. Headache				
d. Nasal congestion				
e. Feeling feverish				
f. Body aches and pains				
g. Fatigue (tiredness)				
h. Neck pain				
i. Interrupted sleep				
j. Wheezing				
k. Coughing up phlegm (sputum)				
l. Short of breath				
m. Loss of appetite				

Impact of the Respiratory Infection**2. During the past 24 hours, how able were you to:**

	No Difficulty	Some Difficulty	Moderate Difficulty	Great Difficulty
a. Get out of bed				
b. Leave your home				
c. Prepare meals / get your own food				
d. Perform usual activities				
e. Concentrate on tasks				
f. Take care of yourself				
g. Go out of the room you are in				

3. During the past 24 hours, have you felt:

	Not at all	Somewhat	Moderately	Extremely
a. Irritable				
b. Helpless				
c. Worried				
d. Frustrated				

4. Since this time yesterday, have you been concerned about:

	Not at all concerned	Somewhat concerned	Moderately concerned	Extremely concerned
a. People worrying about you				
b. Being a burden				
c. People being annoyed with you				
d. Needing to depend on people				
e. People having to do extra things for you				

Respiratory Infection intensity and impact questionnaire (RiiQ™) ©RH Osborne (2006, 2018).
No part of the RiiQ™ may be copied or reproduced in any form without written permission from
RH Osborne PhD: [contact]

(Variable recall Version. English. Administered under license by Janssen Pharmaceuticals).
(English – administration once daily)

